Clinical Investigation Plan

CP348

A randomized, open-labelled, crossover study confirming performance of a new single-use compact intermittent catheter in a population of adult female intermittent catheter users.

June – December 2023

Master

NCT identifier: NCT05814211

Document date: 2023-02-14

CHANGE LOG

VERSION NUMBER	ISSUED BY (INITIALS)	COMMENTS (MAJOR CHANGES SINCE LAST REVISION)
1.0		First approved version
2.0		5.5 Assessments and 5.8 Blinding has been added. 6.4 Screening Failures and Drop-Outs has been changed
3.0		18.7 has been changed to 18.6.1 and 18.8 to 18.6.2

This confidential document is the property of Coloplast A/S.

No unpublished information contained herein may be disclosed without written approval of Coloplast A/S.

SYNOPSIS OF THE CLINICAL INVESTIGATION

Title:

A randomized, open-labelled, crossover study confirming performance of a new single-use compact intermittent catheter in a population of adult female intermittent catheter users.

Investigational device and comparators:

The investigational device is a new single-use compact intermittent catheter, which will be tested in two different sizes - size CH12 and CH14 - for female catheter users. The investigational device is a catheter for single use only and is intended to be used for drainage of the bladder through the urethra.

The investigational devices are not CE-marked, and they will be provided by Coloplast A/S, Denmark.

The comparators are CE-marked SpeediCath Eve and SpeediCath Compact Plus Female in the sizes CH12 or CH14 and will be provided by Coloplast A/S.

Intended use:

The investigational device is a urinary catheter for intermittent use, available in the sizes CH12 and CH14.

The catheter is intended for transient (less than 60 minutes) intermittent drainage of the bladder.

Objective(s):

Primary objective:

[figure not shown]
To demonstrate superiority of the new compact catheter in terms of improved bladder emptying, with the catheterisation performed by a health care professional.

Secondary objectives:

To assess safety and catheter perception of the new compact catheter.

Design of the investigation:

The investigation is a multi-centre, randomised, controlled crossover study including 72 female IC users. The total study duration for the individual subject will be approximately 4 weeks, consisting of four site visits and two 2-week test periods (T) at home (+/- 3 days). Visits 0 and 1 can be performed on the same day. One self-catheterisation will be done at visit 1. For visit 2 and 3, two catheterisations, (one HCP and one self-catheterisation) will be performed in a hospital setting for bladder emptying assessment at each visit. Test periods (at home) take place directly following visit 1 and 2. Visit 3 will terminate the study.

Expected duration of the clinical investigation:

The dates below are approximate, and no subjects will be enrolled before all required approvals have been obtained. If changes are required, applicable EC and regulatory authorities will be notified.

First patient in (FPI)	June-August 2023
Last patient in (LPI)	November 2023
Last patient out (LPO)	December 2023
Database lock (DBL)	January 2024

Endpoint(s):

Primary endpoint

- Residual volume at 1st flow-stop i.e., post catheterisation volume minus volume at 1st flow-stop, both derived from a catheterisation profile (catheterisation performed by a healthcare professional), [g].

Secondary endpoints

- Number of flow-stop episodes derived from a catheterisation profile (catheterisation performed by a healthcare professional), [number].
- Number of flow-stop episodes derived from a catheterisation profile (self-catheterisation), [number]
- Residual volume at first flow-stop i.e., post catheterisation volume minus volume at 1st flow stop, both derived from a catheterisation profile (self-catheterisation), [mL]
- Average residual volume post catheterisation measured with the Bladder Scanner (triplicate measurements) (HCP and self-catheterisation), [mL], (V2, V3)
- Number of Adverse events, [number]

Exploratory endpoints

- Perception questions evaluated on a 5-point scale assessed on V2 and V3 (perception questionnaire)

Population/subjects:

The clinical investigation will be conducted in 72 subjects enrolled at approximately 10-12 clinical investigation sites in Denmark, UK and France. The enrolment is competitive.

To be included in the investigation, the subjects must comply with the selection criteria described below:

Inclusion criteria	Exclusion criteria

1. Is Female2. Is at least 18 years of age and has full legal capacity3. Has signed an informed consent form4. Has used clean intermittent self-catheterisation (CH12 or CH14) for at least one month up to inclusion5. Is using intermittent self-catheterisation for a minimum of 3 times per day for bladder emptying6. Has used a compact catheter 50% of the times (or more) for the last two weeks prior to entering the study7. Has the ability (assessed by investigator) and willingness to follow study procedures	
1. Is participating in any other clinical study during this investigation2. Has previously participated in this study3. Has symptoms of urinary tract infection at the time of inclusion, as judged by the investigator (if the patient recovers within the recruitment period, a second inclusion is allowed, under a different subject id)4. Is an individual with a history of – suspected to be – or showing signs of producing an excessive amount of mucus or large/clustered sediments or debris5. Has any known allergies towards ingredients in the investigational device6. Is pregnant7. Is breastfeeding

LIST OF ABBREVIATIONS

ABBREVIATION	WRITTEN OUT	EXPLANATION (IF APPLICABLE)
ADE	Adverse Device Effect	See section 18.2
AE	Adverse Event	See section 18.1
ASADE	Anticipated Serious Adverse Device Effect	See section 18.4.2
CIP	Clinical Investigation Plan	
CH12	Refers to Catheter Diameter	See section 7.1.1
CH14		
CRF	Case Report Form (paper or electronic)	Questionnaire to be used for data collection
CM	Clinical Manager	
DQF	Data Query Forms	A DQF is a query specifically used in clinical research. The DQF is the primary data query tool from the sponsor to clarify discrepancies and ask the investigator for clarification. The DQF is part of the data validation process in a clinical investigation.
DD	Device deficiency	See section 18.3
EC	Ethics Committee	
eCRF	Electronic Case Report Form	
IB	Investigator's Brochure	Compilation of the current clinical and non-clinical information on the investigational medical device(s,) relevant to the clinical investigation.
IC	Intermittent Catheterisation	
IFU	Instruction For Use	
IRB	Institutional Review Board	
ITT	Intention to Treat	

Urinary tract infections (UTIs) are a common sequela in individuals with lower urinary tract diseases who are dependent on urinary catheters for bladder emptying (Averbeck et al., 2018; De Ridder et al., 2005; Feneley, Hopley, & Wells, 2015; Kennelly et al., 2019; Wyndaele, 2002). Although clean intermittent catheterisation (IC) is considered one of the safest drainage methods, the incidence of catheter associated UTIs is still high with rates between 0.8-3.5 per year (Kennelly et al., 2019). Common risk factors from IC include urethral- and bladder trauma, incomplete bladder emptying and bacterial insertion supporting an environment for infection (Averbeck et al., 2018; Fisher et al., 2018; Kennelly et al., 2019).

Therefore, Coloplast A/S has developed a new intermittent compact catheter for females, to ensure thorough bladder emptying without the need for repositioning and with minimal urethral- and bladder trauma.

The aim of this investigation is to assess performance of this new compact catheter compared to a conventional 2-eyelet catheter.

3 Objective(s) and hypotheses of the clinical investigation

3.1 Objectives

Primary objective:

To demonstrate superiority of the new compact catheter in terms of improved bladder emptying, with the catheterisation performed by a health care professional.

Secondary objectives:

To assess safety and catheter perception of the new compact catheter.

3.2 Hypothesis

The aim is to assert the hypothesis of superior performance of the compact catheter compared to conventional compact 2-eyelet catheters.

4 Investigational device and comparator(s)

4.1 Description of investigational device

The investigational device is a ready-to-use, sterile, hydrophilic-coated female compact catheter for intermittent catheterisation, available in the sizes CH12 and CH14. The device is for single use only and is intended to be used for drainage of the bladder through the urethra by people with missing or reduced bladder control.

The device is intended to be used by female catheter users in this clinical study.

[figure not shown]

Figure 1. Illustrates the investigational device used in the study

4.2 Identification and traceability of the device

All investigational devices are labelled as per regulations and include "Exclusively for Clinical Investigational" on the label. The devices are also identified with study number, device name/code, and item/lot number and are accounted for through a sponsor accountability log.

Upon EC/CA approval, investigational devices will be shipped to the principal investigator or delegate. Additionally, all investigational devices will be accounted for and documented on a site accountability log. The receipt and disposition of all investigational devices will be verified through monitoring. All unused devices will be returned to Coloplast at the conclusion of the study.

4.3 Intended use of the device in the clinical investigation

The catheter is intended for transient (less than 60 minutes) intermittent drainage of the bladder.

4.4 Intended population for the device

The eligible population is female intermittent compact catheter (IC) users who are depending on IC for drainage of the bladder. This population will be eligible to use the newly developed device when it becomes commercially available.

There are no proposed contraindications.

4.5 Handling of the investigational device

The handling of the investigational device is described in detail in the Instruction for Use (IFU) accompanying the devices. It is stated in the IFU that the investigational devices are for single-use and must be stored away from direct sunlight. Reprocessing, washing, disinfection, and sterilisation may compromise device characteristics, causing additional risk of physical harm to, or infection of, the user.

All Principal Investigators and delegates will receive training by the sponsor and/or principal investigator in the handling and correct use of the investigational devices. All training will be documented.

For further details regarding the Investigational device, please refer to the Investigators Brochure VV-0518890.

4.6 Total number of devices intended for the clinical investigation

72 subjects will be included in the study. Subjects will be supplied with sufficient amount of test products to accommodate their usual catheterisation procedure for each test period. The investigational devices and comparators are packed in retail boxes with 30 products in each.

Example: The test period (home-use) is 2 weeks (14 days) and with an estimated usage of 6 catheters/day it equals 84 catheters, so subject will receive 3 retail boxes for home use (90 catheters) for each test period.

4.7 Description of the comparator products

Two comparators: SpeediCath Compact Eve and SpeediCath Compact Plus Female, sizes CH12 or CH14. Both comparators are CE-marked Coloplast products and will be provided by Coloplast A/S.

As the comparator devices are already on the market and will be used within the intended use in this investigation, it is not considered an investigational device according to ISO 14155:2020 and is thus not described into further details here.

5 Design of the clinical investigation

5.1 General

The investigation is a multi-centre, multi-national, randomised, controlled crossover study including 72 female IC users.

The total study duration for the individual subject will be approximately 4 weeks, consisting of four site visits and two 2-week test periods (T1 and T2) at home (+/- 3 days). Visits 0 and 1 can be performed on the same day. One self-catheterisation will be done at visit 1 with the first randomised product. For visit 2 and 3, two catheterisations (HCP and a self-catheterisation) will be performed in a hospital setting for bladder emptying assessment at each visit. At visit 2 the catheterisations will be done with the first randomised product, and at visit 3 the catheterisations will be done with the second randomised product. Test periods (at home) take place directly following visit 1 and 2. No data will be collected in the test periods at home. Visit 3 will terminate the study.

The study design and procedures are described below in figure 1.

[figure not shown]

Figure 1. Study design

5.2 Primary endpoints

- Residual volume at 1st flow-stop i.e., post catheterisation volume minus volume at 1st flow-stop, both derived from a catheterisation profile (catheterisation performed by a healthcare professional), [mL]. (V2, V3)

5.3 Secondary Endpoints

- Number of flow-stop episodes derived from a catheterisation profile (catheterisation performed by a healthcare professional), (V2, V3) [number]
- Number of flow-stop episodes derived from a catheterisation profile (self-catheterisation), (V2, V3), [number]
- Residual volume at 1st flow-stop i.e., post catheterisation volume minus volume at 1st flow-stop, both derived from a catheterisation profile (self-catheterisation), (V2, V3), [mL]
- Average residual volume post catheterisation measured with the BladderScanner (triplicate measurements) (V2, V3) for both self-catheterisation and for HCP catheterisation, [mL]
- Number of Adverse events, [number]

5.4 Exploratory endpoints

- Perception questions evaluated on a 5-point scale assessed on V2 and V3 (perception questionnaire), see appendix A; Perception questionnaire based on perception of catheterisations in test period leading up to the visit

5.5 Assessments

Assessments collected in a hospital setting

(Catheterisation by HCP and self-catheterisation):

- Position of the subject when performing the catheterisation, [sitting/standing] (V1, V2, V3)
- Catheter used for catheterisation [investigational product/comparator, including product size (CH12/CH14)] (V1, V2, V3)
- Discomfort at insertion measured using the visual analogue scale (VAS) (only self-catheterisation), [cm], (V2, V3)
- Discomfort at withdrawal measured using the VAS (only self-catheterisation) (V2, V3)
- Discomfort during emptying of bladder measured using the VAS (only self-catheterisation) (V2, V3)
- Discomfort at end of emptying the bladder measured using the VAS (only self-catheterisation) (V2, V3)
- Urine volume at 2nd until 10th flow stop (derived from catheterisation profile), [mL] (V2, V3)
- Urine volume measured post catheterisation (derived from catheterisation profile), [mL] (V2, V3)
- Residual volume pre catheterisation measured with the Bladder Scanner (triplicate measurements that must be more than 150 ml to proceed) (V2, V3), [mL]

Other assessments

- Investigational device used in the test period (Test product/Comparator), including size (CH12/CH14))
- Device Deficiencies
- Data for complaint reporting (Vigilance) (for Adverse Device Effects, Device Deficiencies and Serious Adverse Device Effects reported in CE-marked Coloplast products in the investigation.
-

Backup (redundant) measurements by HCP in case of missing profile readout:

- Urine volume at 1st flow stop (scale), [g].
- Urine volume measured post catheterisation (scale), [g].
- Time for start of catheterization ([HH+:nn],[hours and minutes]
- Number of flow-stop episodes counted by HCP, [number]

5.6 Rationale for selection and measurement of endpoints

The endpoints have been selected based on the evaluation of performance of the new catheter features in terms of efficiency of catheter-associated bladder emptying and degree of catheter-associated microtrauma. Both inadequate bladder emptying and urethral/urothelial microtrauma, are important risk factors for UTI (Kennelly et al., 2019).

Flow-stops: A common process of IC is the repositioning of the catheter towards the end of drainage to ensure thorough bladder emptying (Vahr S., 2013). The rationale behind this process is that as the bladder empties with a standard 2-eyelet catheter, the bladder wall deflates around the drainage holes, causing bladder mucosa to be sucked into the eyelets, withholding urine to exit. In 1965, mucosal suction and consequently mucosal microtrauma was first described with an indwelling Foley catheter (Milles, 1965) and later reproduced in several other settings (Glahn, 1988; Glahn, Braendstrup, & Olesen, 1988; Grocela & Jura, 2010). The event has been reproduced with intermittent catheters in a porcine bladder model in a pre-clinical setting at Coloplast (Tentor, 2022) and exploratory clinical activities involving healthy subjects and IC-users (both male and female) have demonstrated a significantly reduced number of flow-stops with the new micro-hole catheter compared to conventional 2-eyelet catheters (Coloplast A/S, 2021a).

Residual volume at 1st flow-stop: As a consequence of mucosal suction, urine flow may come to a halt prematurely, i.e. before the bladder is thoroughly emptied, hence the need to adjust the catheter (e.g. repositioning) to ensure that urine starts to flow again. The aim with the micro-hole drainage is to avoid mucosal suction, thereby securing a thorough bladder emptying at the first sensation of a flow-stop.

Therefore, residual urine volume at 1st flow-stop (RV1) represent the volume left in the bladder for those IC-users who perceive a flow-stop as an emptied bladder and therefore withdraws the catheter prematurely. RV1 is a technical/theoretical term and is thought to be a contributing factor to any other residual urine left in the bladder after catheterisation.

RV1 is measured *in* catheterisation by HCP and by self-catheterisation as it allows for comparison between catheters during an expectedly correctly applied catheterisation technique.

5.7 Equipment/methods and timing for assessing the variables.

Scales for measurement of total amount of urine, ultrasound scanner measuring residual urine [BladderScan i10, Verathon Inc.], databox, container, funnel for urine collection and pregnancy tests will be provided by Coloplast A/S.

5.8 Randomisation Procedure

All subjects that have given informed consent and meet the inclusion and exclusion criteria will be randomised.

This investigation involves two treatments, the investigational device, and the comparator devices

The Rave RTSM™ is a validated randomization solution, that will be used for the randomization in this investigation. A centralized randomization will be implemented, in which, participants are to be randomly assigned to two intervention sequences in block sizes of 8.

For technical reasons, to ensure correct randomization in an equal split between treatment arms, the two treatment arms are technically implemented as illustrated below.

Treatment A: Investigational Device × Comparator 1 (SpeediCath Compact Eve) (25%)

Treatment B: Investigational Device × Comparator 2 (SpeediCath Compact Plus Female) (25%)

Treatment C: Comparator 1 (SpeediCath Compact Eve) × Investigational Device (25%)

Treatment D: Comparator 2 (SpeediCath Compact Plus Female) × Investigational Device (25%)

Randomisation will be 2:1:1 (Investigational device: Comparator: SpeediCath Compact Eve: SpeediCath Compact Plus Female)

5.9 Blinding

Subjects will not be blinded in this investigation due to inclusion of self-catheterisation. Furthermore, personnel present at the catheterisation i.e. nurses and assisting Coloplast Clinical Managers, Data Management Specialists and CRAs are also not blinded. All other Coloplast personnel i.e. the Statistician, the specialists analysing the catheterisation profiles and Project Manager will be blinded until the data base lock.

5.10 Total expected duration of the clinical investigation

The dates below are approximate, and no subjects will be enrolled before all required approvals have been obtained. If changes are required, applicable IRB/EC and regulatory authorities will be notified.

First patient in (FPI)	June 2023
Last patient in (LPI)	November 2023
Last patient out (LPO)	December 2023
Database lock (DBL)	January 2024

6 Clinical Investigation population

The clinical investigation will be conducted in 72 subjects enrolled in 10 clinical investigation sites in Denmark, UK and France.

To be included in the investigation, the subjects must comply with the selection criteria described below.

6.1.1 Inclusion criteria

For a subject to be eligible, all inclusion criteria must be answered "yes":

Inclusion criteria	Justification for inclusion criteria
1. Is Female	Intended patient population of investigational and comparator devices.
2. Is at least 18 years of age and has full legal capacity	Intended patient population of investigational and comparator devices.
3. Has signed an informed consent form	To meet Helsinki Declaration.
4. Has used clean intermittent self-catheterisation (CISC) (CH12 or CH14) for at least one month up to inclusion	To ensure that the subject has been given written and oral information regarding the investigation and know enough about the investigation to decide on participation.
5. Is using intermittent self-catheterisation for a minimum of 3 times per day for bladder emptying	To ensure voluntariness and that Helsinki Declaration is met.
6. Has used a compact catheter 50% of the time (or more) for the last two weeks prior to entering the study	To ensure that the subject is used to catheterisation
7. Has the ability (assessed by investigator) and willingness to follow study procedures	To ensure that the subject is used to catheterisation.
	To ensure that the subject is able to use compact catheters.
	To ensure sufficient data for successful completion of the study.

6.1.2 Exclusion criteria

For an eligible subject, all exclusion criteria must be answered "no":

Exclusion criteria	Justification for exclusion criteria
1. Is participating in any other clinical study during this investigation	To eliminate uncertainty whether any Adverse Events (AE's) or Serious Adverse Events (SAE's) occurring during the investigation relate to the usage of the herein tested devices. Also, to eliminate unintentional effect from other devices/medicines on the investigation's data.
2. Has previously participated in this study	To ensure integrity of results.
3. Has symptoms of urinary tract infection at time of inclusion, as judged by the investigator (if the	To ensure subject safety and integrity of results.

patient recovers within the recruitment period, a second inclusion is allowed, under a different subject id)	
4. Is an individual with a history of - suspected to be – or showing signs of producing an excessive amount of mucus or large/clustered sediments or debris	To ensure subject safety and integrity of results.
5. Has any known allergies towards ingredients in the investigational device	To ensure subject safety and integrity of results.
6. Is pregnant	Even though the ingredients and the recipes have been approved for human beings, their effect on embryos, foetuses and infants are unknown
7. Is breastfeeding	Even though the ingredients and the recipes have been approved for human beings, their effect on embryos, foetuses and infants are unknown

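### Exclusion 5 screens for allergy to the investigational device only, although every woman is also assigned one of two comparators; its scope should be stated to match the products assigned

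*Combined protocol and SAP*

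**What the plan says.** Section 6.1.2 introduces its list with "For an eligible subject, all exclusion criteria must be answered" in the negative. Item 5 on that list is "Has any known allergies towards ingredients in the investigational device", and the reason given beside it is "To ensure subject safety and integrity of results". The synopsis carries the same item in the same words. No other inclusion or exclusion criterion mentions allergy.

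Section 4.7 names two comparators, SpeediCath Compact Eve and SpeediCath Compact Plus Female. Because they are marketed and used within their intended use, it says of the comparator that "it is not considered an investigational device according to ISO 14155:2020", and for that reason it does not describe them further. Section 5.8 treats the investigational device and the comparator devices as two treatments and lists four sequences of 25% each. Every sequence pairs the investigational device with one comparator.

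Usage of the term varies elsewhere. Section 14 (device accountability) expressly counts comparators among the investigational devices. Section 5.5 records the investigational device used in a test period as either test product or comparator.

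**The concern.** An allergy criterion would normally cover everything that the protocol requires a subject to use. Here it names one of the two treatments. If a site takes section 4.7 at its word, a woman with a documented allergy to a comparator-only ingredient answers exclusion 5 in the negative, passes screening and may be randomised to that comparator.

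The main thing at stake is avoidable exposure of someone whose allergy is already known. The secondary stake is data. She might stop during the comparator period and leave no comparator measurement, which costs a within-subject pair in a crossover. Any reaction would also appear in the adverse-event, discomfort or perception summaries.

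**Working it through.** No sample-size or error-rate formula applies, and the plan gives no figure to reproduce. The check is a reading of the relevant sections together, with simple arithmetic on exposure.

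**1. Who is assigned a comparator (section 5.8)**

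| Sequence | First product | Second product | Share |
|---|---|---|---|
| A | Investigational | Compact Eve | 25% |
| B | Investigational | Compact Plus Female | 25% |
| C | Compact Eve | Investigational | 25% |
| D | Compact Plus Female | Investigational | 25% |

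- Any comparator: 25% + 25% + 25% + 25% = 100%.
- Compact Eve (A + C): 25% + 25% = 50%, or 36 of the planned 72.
- Compact Plus Female (B + D): 25% + 25% = 50%, also 36 of 72.

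A woman allergic to an ingredient of one comparator only would therefore be assigned that product with probability 50%. If the ingredient is in both comparators, the probability is 100%.

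**2. How much comparator use is planned**

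- Home use is one two-week period (± 3 days) per product (section 5.1).
- At the supply example in section 4.6, 6 per day × 14 days = 84 uses. At the inclusion minimum of 3 per day, 3 × 14 = 42.
- Site use under section 7.2: in A and B, one HCP catheterisation and one self-catheterisation at V3, so 2. In C and D, one self-catheterisation at V1 plus two catheterisations at V2, so 3.

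These figures describe exposure of all subjects. They do not count allergic subjects or harm.

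**3. Does exclusion 5 reach the comparators?**

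- *Narrow reading.* Section 4.7 denies the comparators that status. Section 5.8 lists the two treatments separately. Exclusion 5 uses the singular. Where the plan means both products it tends to say so: the justifications for inclusion 1 and 2 and the safety definitions in 18.1 to 18.3 name the comparator as well.
- *Broad reading.* Sections 14 and 5.5 use the term to include comparators. The flow-chart in 7.3 has investigational devices handed out at both V1 and V2, although each subject receives the investigational device at only one of those visits.

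The narrow reading is the more natural one for exclusion 5. The plan's own usage still leaves room for a site to take the other.

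**4. Does anything else close the gap?**

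- Inclusion 6 asks for recent use of a compact catheter of any make. The baseline form in 7.2 lists several other manufacturers, so earlier tolerance of a comparator is not assured.
- Inclusion 7 concerns ability and willingness, not allergy.
- Relevant medical history is taken at V1, but no rule ties it to eligibility.
- Withdrawal under 6.3 acts after enrolment. Section 6.4 removes subjects who fail the criteria, and this woman passes them.

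**5. Timing**

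At V1 the criteria are checked first, randomisation follows, and the first product is then introduced and used. The comparator is unknown when eligibility is settled, so a criterion that names only the comparator eventually assigned could not be applied.

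**6. Reach into the analysis**

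The primary endpoint is residual volume at first flow-stop during HCP catheterisation, and nothing in the documents links allergy to it. The calculation in 10.7 uses no quantity that depends on this criterion. Adverse events (10.4, 10.6) and perception (10.5) are listed or summarised without a hypothesis test, and VAS discomfort is an assessment (5.5).

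**The case against.** The strongest reply is that the gap may be empty. The criterion concerns ingredients. If the comparators contain nothing that the investigational device lacks, exclusion 5 already protects against both. The text reviewed gives no composition for any product, so this cannot be settled from the documents. The reply stands as a condition on the point.

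A second reply is that section 4.7 explains why the comparators are not described and does not define terms for eligibility, while sections 5.5 and 14 include them. This stands in part. It makes the wording ambiguous rather than plainly deficient, but an eligibility question that sites may answer in two ways still needs correcting.

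A third is that medical history, investigator judgement and the withdrawal rules would catch most cases. They may help, but none is an allergy exclusion.

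A reader might infer something stronger: that screening out reactors to one product only tilts the safety and perception results towards the investigational device. The documents do not support that. Recruitment draws partly on the sponsor's database with selection on product usage (6.2.1), and the baseline form lists both comparators as possible current products. Women already using a comparator are selected for tolerating it. The investigational device is not CE-marked and is not on that list. This selection works the other way, and the share of such women is not given, so the net direction is unknown.

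**Conclusion.** The point holds as a small safety and eligibility correction. On a literal reading, exclusion 5 is narrower than the exposure that the protocol assigns to every subject, and its stated purpose gives no reason for the difference. The conclusion assumes the narrow reading of the term and at least one ingredient present in a comparator and absent from the investigational device. Without that ingredient, the wording is untidy but nobody is exposed to an unscreened allergen.

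The number of women affected is probably small, and the documents give no allergy frequency from which to estimate it. The 100% assigned a comparator and the 84 uses should not be read as measures of harm. The primary analysis and power are unaffected. Neither a directional bias nor a predictable excess of comparator drop-outs is demonstrated.

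**What to change.** Reconcile exclusion 5 in the synopsis, section 6.1.2 and the eCRF with sections 4.7, 5.8 and 14, so that the scope of the allergy criterion explicitly matches all products a subject may be assigned. Because allocation follows the eligibility check, that scope has to include SpeediCath Compact Eve and SpeediCath Compact Plus Female together. At the same time, use one meaning of investigational device throughout, including section 5.5 and the flow-chart in 7.3. The sponsor supplies all three products and is well placed to check whether their ingredients differ. If they do not, the edit only removes the ambiguity.

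The cost is a few words in the plan and the eCRF, and possibly one or two more screen failures. No change to the sample size or the analysis is needed.
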